Immunogenicity testing will include performing HAI and Neut antibody assays against the 2017 H7N9 vaccine virus on serum samples collected for Group 1 on Days 1 (baseline), 22, and 43, and at approximately 180 days post second adjuvanted 2017 H7N9 IIV dose (Day 202), and for Group 2 on Study Days 22 (baseline), 43, and 64, and at approximately 180 days post second 2017 H7N9 IIV adjuvanted dose (Day 223). Serological antibody assays will be performed against the vaccine viruses in IIV4 from serum samples collected at baseline (Day 1) and approximately 21 and 180 days following receipt of seasonal IIV4 (Groups 1, 2, and 3).

Novel methods for identifying and assessing alternative correlates of protection against influenza infection are needed. To assess the NA-specific antibody response to vaccination, it is first necessary to determine the NA content of inactivated influenza vaccine; this assay is

under development. If successful, the NA content in a dosage-specific manner can be correlated to the N9 NA-specific antibody responses elicited by the 2017 H7N9 IIV.

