4.5.2. Immunogenicity Variables

Individual HAI and Neut results will be reported by the central immunology laboratory for the homologous 2017 A/H7N9 vaccine strain, A/Hong Kong/125/2017, the homologous strains in the seasonal 2017/2018 IIV4 Fluzone vaccine (A/Michigan/45/2015 X-275 (H1N1), A/Hong Kong/4801/2014 X263B(H3N2), B/Phuket/3073/2013 (B Yamagata lineage), and B/Brisbane/60/2008 (B Victoria lineage)). Assay results are reported as a reciprocal titer with values of $10 \cdot 2^k$, where $k=0, 1, 2$, etc. The lower limit of detection for the HAI and Neut assays is 1:10; values below the limit of detection are reported as '<10', and for analysis are imputed as one-half the limit of detection ($10/2 = 5$). For analysis, the geometric mean (calculated on natural log scale) of repeated results for each sample will be computed and used as the response for all subsequent calculations. The variation arising from multiple measurements for an individual at a single time point is not used in subsequent calculations. See Section 3.3 for definitions of derived variables for the analysis of HAI and Neut data.

The assay to determine the influenza virus N9 Neuraminidase (NA) antibody response to vaccination is under development. An addendum to the SAP will be generated to outline the planned analyses when assay development is complete.

For subjects in Group 1 (Simultaneous Administration) there is potential for an overlap between the windows for Visit 9 (Day 181 post vaccination 1 ± 14 days) and Visit 10 (Day 181 post vaccination 2 ± 14 days). Should a subject complete both visits on the same date, HAI and Neut results against the seasonal IIV4 vaccine strains on that date will be associated with Visit 9, while HAI and Neut results against the 2017 H7N9 vaccine strain on that date will be associated with Visit 10.

All immunogenicity data will be uploaded into the SDCC's electronic data capture system.

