6.3.2. Modified Intention-to-Treat (mITT) Population

The modified intent-to-treat (mITT) population includes all subjects who received at least one dose of study vaccine and contributed both pre- and at least one post-study vaccination venous blood samples for immunogenicity testing (HAI or Neut antibody assays) for which valid results were reported. For analyses using the mITT population, subjects in Group 2 who discontinue treatment after receiving the single IIV4 dose (Dose 1) but prior to receiving the first dose of the H7N9 vaccine (Dose 2) will be analyzed with group 3. All other subjects will be grouped based on randomized treatment group.

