8.1. Primary Immunogenicity Analysis

The primary immunogenicity endpoints HAI and Neut seroconversion, percentage of subjects with titer $\geq 1:40$, and GMTs against the seasonal IIV4 strains 21 days after the IIV4 vaccination for all groups and against the homologous A/H7N9 vaccine strain 21 days after the second dose of AS03 adjuvanted 2017 H7N9 IIV will be summarized as described above. The primary analysis population will be mITT, with results from the PP population providing a comparison of the sensitivity of immunogenicity results to subject adherence to protocol-

defined conditions. Regression modelling of seroconversion and log titers is planned as described in Section 8.3.2.

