transformation, multiple linear regression will be fit to examine the relationship of log transformed titers at 21 or 180 days after the dose of interest (second dose of AS03 adjuvanted A/H7N9 IIV for the 2017 A/H7N9 strain; IIV4 vaccination for the seasonal IIV4 strains) with treatment schedule. All models will be fit with and without adjustment for the following covariates (Z): age in years, sex (female, male), BMI (<30 , ≥ 30), and prior receipt of seasonal influenza vaccine (did not receive 2016-2017 seasonal vaccine, received 2016-2017 seasonal vaccine). The models as shown below assume a linear relationship between age in years and both probability of seroconversion and GMT. The validity of this assumption will be assessed prior to analysis and, if the relationship between age and response is found to be non-linear, adjustments will be made to model parameters to satisfy regression assumptions. Modeling assumptions will be checked using standard diagnostic methods (e.g., using the INFLUENCE option in PROC LOGISTIC or PROC GLM). Parameter estimates and odds ratio estimates for the logistic models will be presented for the 2017 A/H7N9 strain without covariate adjustment in [Table 68](#), [Table 69](#), [Table 70](#), [Table 71](#), and with covariate adjustment in [Table 76](#), [Table 77](#), [Table 78](#), [Table 79](#); and for the seasonal IIV4 strains without covariate adjustment in [Table 72](#), [Table 73](#), [Table 74](#), [Table 75](#), and with covariate adjustment in [Table 80](#), [Table 81](#), [Table 82](#), [Table 83](#). Parameter estimates for the multiple linear regression models will be presented for the 2017 A/H7N9 strain without covariate adjustment in [Table 84](#), [Table 85](#), [Table 86](#), [Table 87](#), and with covariate adjustment in [Table 92](#), [Table 93](#), [Table 94](#), [Table 95](#); and for the seasonal IIV4 strains without covariate adjustment in [Table 88](#), [Table 89](#), [Table 90](#), [Table 91](#), and with covariate adjustment in [Table 96](#), [Table 97](#), [Table 98](#), [Table 99](#).

Model 1A: Logistic Regression (without covariate adjustment):

$$\text{logit}[P(\text{seroconversion})] = \beta_0 + \beta_1 \times \text{Treatment} + \varepsilon$$

Model 1B: Logistic Regression (with covariate adjustment):

$$\text{logit}[P(\text{seroconversion})] = \beta_0 + \beta_1 \times \text{Treatment} + \beta_2 \times Z + \varepsilon$$

Model 2A: Multiple Linear Regression (without covariate adjustment):

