$$\log(\text{titer}) = \beta_0 + \beta_1 \times \text{Treatment} + \varepsilon$$

Model 2B: Multiple Linear Regression (with covariate adjustment):

$$\log(\text{titer}) = \beta_0 + \beta_1 \times \text{Treatment} + \beta_2 \times Z + \varepsilon$$

Subjects missing data for one or more covariates will be excluded from Models 1B and 2B.

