Table 86: Multiple Linear Regression Model to Evaluate the Relationship of Administration Schedule with Log-Adjusted Neut Titer against 2017 A/H7N9 at 21 Days Post Second Dose of AS03 adjuvanted A/H7N9 Vaccine, Per Protocol Population*

Table 87: Multiple Linear Regression Model to Evaluate the Relationship of Administration Schedule with Log-Adjusted Neut Titer against 2017 A/H7N9 at 180 Days Post Second Dose of AS03 adjuvanted A/H7N9 Vaccine, Per Protocol Population

Table 88: Multiple Linear Regression Model to Evaluate the Relationship of Administration Schedule with Log-Adjusted HAI Titer against Seasonal IIV4 Strains at 21 Days Post IIV4 Vaccination, Per Protocol Population*

Model Parameter	Parameter Category	Parameter Estimate	SE	95%CI	p-value
A/Michigan/45/2015 X-275 (H1N1)					
Intercept	N/A	xxx.x	xxx.x	-	x.xxx
Treatment	Simultaneous Administration (reference)	-	-	-	-
	Sequential Administration	xxx.x	xxx.x	xx.x-xx.x	x.xxx
	IIV4 Only	xxx.x	xxx.x	xx.x-xx.x	x.xxx
[Repeat for all IIV4 Strains]					
N = XX (Number of subjects in the Per Protocol Population) n = XX (number of subjects with results available at 21 days post IIV4 vaccination in the per protocol population). XX subjects missing covariate data were excluded from this analysis.					

Tables with similar format:

Table 89: Multiple Linear Regression Model to Evaluate the Relationship of Administration Schedule with Log-Adjusted HAI Titer against Seasonal IIV4 Strains at 180 Days Post IIV4 Vaccination, Per Protocol Population

Table 90: Multiple Linear Regression Model to Evaluate the Relationship of Administration Schedule with Log-Adjusted Neut Titer against Seasonal IIV4 Strains at 21 Days Post IIV4 Vaccination, Per Protocol Population*

Table 91: Multiple Linear Regression Model to Evaluate the Relationship of Administration Schedule with Log-Adjusted Neut Titer against Seasonal IIV4 Strains at 180 Days Post IIV4 Vaccination, Per Protocol Population

Table 92: Multiple Linear Regression Model to Evaluate the Relationship of Administration Schedule with Log-Adjusted HAI Titer against 2017 A/H7N9 at 21 Days Post Second Dose of AS03 adjuvanted A/H7N9 Vaccine, Adjusted for Baseline Covariates, Per Protocol Population*

Model Parameter	Parameter Category	Parameter Estimate	SE	95%CI	p-value
Intercept	N/A	xxx.x	xxx.x	-	x.xxx
Treatment	Simultaneous Administration (reference)	-	-	-	-
	Sequential Administration	xxx.x	xxx.x	xx.x-xx.x	x.xxx
Age (years)	N/A	xxx.x	xxx.x	xx.x-xx.x	x.xxx

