Sex	Female (reference)	-	-	-	-
	Male	xxx.x	xxx.x	xx.x-xx.x	x.xxx
BMI	<30 (reference)	-	-	-	-
	≥30	xxx.x	xxx.x	xx.x-xx.x	x.xxx
Prior Receipt of Influenza Vaccine	Did Not Receive 2016-2017 Seasonal Influenza Vaccine (reference)	-	-	-	-
	Received 2016-2017 Seasonal Influenza Vaccine	xxx.x	xxx.x	xx.x-xx.x	x.xxx

N = XX (Number of subjects in the Per Protocol Population)
n = XX (number of subjects with results available at 21 days post IIV4 vaccination in the per protocol population).
XX subjects missing covariate data were excluded from this analysis.

Tables with similar format:

Table 93: Multiple Linear Regression Model to Evaluate the Relationship of Administration Schedule with Log-Adjusted HAI Titer at 180 Days Post Second Dose of AS03 adjuvanted A/H7N9 Vaccine, Adjusted for Baseline Covariates, Per Protocol Population

Table 94: Multiple Linear Regression Model to Evaluate the Relationship of Administration Schedule with Log-Adjusted Neut Titer at 21 Days Post Second Dose of AS03 adjuvanted A/H7N9 Vaccine, Adjusted for Baseline Covariates, Per Protocol Population*

Table 95: Multiple Linear Regression Model to Evaluate the Relationship of Administration Schedule with Log-Adjusted Neut Titer at 180 Days Post Second Dose of AS03 adjuvanted A/H7N9 Vaccine, Adjusted for Baseline Covariates, Per Protocol Population

Table 96: Multiple Linear Regression Model to Evaluate the Relationship of Administration Schedule with Log-Adjusted HAI Titer against Seasonal IIV4 Strains at 21 Days Post IIV4 Vaccination, Adjusted for Baseline Covariates, Per Protocol Population*

Model Parameter		Parameter Estimate	SE	95%CI	p-value
A/Michigan/45/2015 X-275 (H1N1)					
Intercept	N/A	xxx.x	xxx.x	-	x.xxx
Treatment	Simultaneous Administration (reference)	-	-	-	-
	Sequential Administration	xxx.x	xxx.x	xx.x-xx.x	x.xxx
	IIV4 Only	xxx.x	xxx.x	xx.x-xx.x	x.xxx
Age (years)	N/A	xxx.x	xxx.x	xx.x-xx.x	x.xxx
Sex	Female (reference)	-	-	-	-
	Male	xxx.x	xxx.x	xx.x-xx.x	x.xxx
BMI	<30 (reference)	-	-	-	-
	≥30	xxx.x	xxx.x	xx.x-xx.x	x.xxx
Prior Receipt of Influenza Vaccine	Did Not Receive 2016-2017 Seasonal Influenza Vaccine (reference)	-	-	-	-
	Received 2016-2017 Seasonal Influenza Vaccine	xxx.x	xxx.x	xx.x-xx.x	x.xxx
[Repeat for all IIV4 Strains]					
N = XX (Number of subjects in the Per Protocol Population) n = XX (number of subjects with results available at 21 days post IIV4 vaccination in the per protocol population). XX subjects missing covariate data were excluded from this analysis.					

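### The linear titer models for the seasonal (IIV4) strains leave out the Day 1 titer, although it is measured in every group, so the schedule effect is less precise than it could be and carries chance baseline imbalance

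*SAP*

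**What the plan says.** SAP 8.3.2 regresses the log titer at 21 or 180 days after the relevant dose on treatment schedule. Model 2A has treatment only. Model 2B adds a vector Z, introduced as "All models will be fit with and without adjustment for the following covariates (Z): age in years, sex (female, male), BMI" in two categories, and ending with 2016-2017 seasonal vaccination (yes or no). The list is closed. Complete cases are used: "Subjects missing data for one or more covariates will be excluded from Models 1B and 2B".

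The shells follow this. Tables 88-91 cover Model 2A for the IIV4 strains (Table 88: "Log-Adjusted HAI Titer against Seasonal IIV4 Strains at 21 Days Post IIV4 Vaccination, Per Protocol Population"). Tables 96-99 cover Model 2B (Table 96: "Seasonal IIV4 Strains at 21 Days Post IIV4 Vaccination, Adjusted for Baseline Covariates, Per Protocol Population"). Table 96 has rows for treatment, age, sex, BMI and prior vaccination only.

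The Day 1 titer is available. SAP 4.1 states "Serological antibody assays will be performed against the vaccine viruses in IIV4 from serum samples collected at baseline (Day 1") and again about 21 and 180 days after IIV4, in Groups 1, 2 and 3. SAP 6.3.2 admits to the mITT population only subjects who "contributed both pre- and at least one post-study vaccination venous blood samples for immunogenicity testing (HAI or Neut antibody assays") with valid results, and SAP 6.3.3 makes PP a subset of mITT.

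SAP 8.1, the primary immunogenicity section, refers to these models: "Regression modelling of seroconversion and log titers is planned as described in Section 8.3.2". SAP 6.7 pools sites in every analysis, although SAP 4.4.3 stratifies randomisation by site.

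**The concern.** The trial asks whether giving the two vaccines together interferes with the response to either (SAP 2). For titers as a continuous outcome, these regressions are the only planned comparison between schedules. Fold rise is defined in SAP 3.3 but is not modelled, and no analysis uses change from baseline.

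Adults may already have antibody to seasonal strains. The protocol allows and records vaccination in earlier seasons, and the seroconversion definition has a branch for starting titers of 1:10 or more. SAP 8.3.1 expects little or no pre-existing antibody for H7N9 and says nothing similar for IIV4. Baseline titer is therefore a likely predictor of the post-vaccination titer for the IIV4 strains in particular.

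Randomisation is stratified by site only, so baseline titer is balanced only by chance. With about 50, 50 and 25 evaluable subjects, a chance difference can be large enough to matter. Tables 32-35 would show it, but no titer model would correct for it.

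A lesser point concerns site. The reason given in SAP 6.7, standard procedures and a central laboratory, covers differences in assessment but not differences in who each site enrols. Leaving out a stratification factor does not bias the estimate. It makes the standard errors slightly too wide if sites differ.

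**Working it through.** **The plan's own figures.** The documents state no SD, precision or power for the log-titer models. The nearest figure is Protocol Table 6 (SAP Table 11): minimum detectable decrease in responders for the IIV4 strains, 75 vs 50, 80% power, two-sided likelihood ratio test at 0.05. Exact binomial enumeration gives 0.228, 0.244, 0.251, 0.250, 0.234 and 0.196 for comparator rates 0.40 to 0.90. These round to the stated 0.23, 0.24, 0.25, 0.25, 0.23 and 0.20, so the table reproduces.

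**Inputs for the titer models**

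- Evaluable subjects: 50, 50 and 25 (Protocol 11.4.2; 60 × 0.85 = 51, 30 × 0.85 = 25.5).
- Contrasts: the shells compare Sequential and IIV4 Only separately with Simultaneous, so 50 vs 50 and 50 vs 25, not the pooled 75 of Table 6.
- Assumed, not in the documents: SD of 2 log2 units; correlation r between Day 1 and post-vaccination log titer of 0.3, 0.5 or 0.7.

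**Standard error and power against Model 2A.** Adding baseline multiplies the SE by √(1 − r²) = 0.954, 0.866, 0.714, a cut of 5%, 13% or 29%. SE = 2 × √(1 − r²) × √(1/50 + 1/n₂). Power is for a two-fold GMT ratio (1 log2 unit), noncentral t, two-sided 0.05, df 122 unadjusted and 121 adjusted.

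| r | SE, 50 vs 50 | Power | SE, 50 vs 25 | Power |
|---|---|---|---|---|
| no baseline term | 0.400 | 70% | 0.490 | 53% |
| 0.3 | 0.382 | 74% | 0.467 | 57% |
| 0.5 | 0.346 | 82% | 0.424 | 65% |
| 0.7 | 0.286 | 94% | 0.350 | 81% |

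**Against Model 2B.** Suppose Z explains a share R² of log-titer variance, assumed 0.05-0.15, and acts only through baseline. The SE multiplier is √[(1 − max(r², R²)) / (1 − R²)].

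- r = 0.3: R² cannot exceed r² = 0.09 here. √(0.91/0.95) = 0.98 at R² = 0.05 and 1.00 at R² = 0.09, a cut of 0-2%.
- r = 0.5: √(0.75/0.95) = 0.89 and √(0.75/0.85) = 0.94, a cut of 6-11%.
- r = 0.7: √(0.51/0.95) = 0.73 and √(0.51/0.85) = 0.77, a cut of 23-27%.

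A separate simulation of 50/50/25 subjects, with two-fold dilution titers floored at 5 and prior vaccination as a partial proxy for baseline, compared Z alone with Z plus baseline. The SE for Group 2 vs 1 (natural log, SD 1.2) fell from 0.244 to 0.236, from 0.242 to 0.218 and from 0.240 to 0.186, that is by 3%, 10% and 23% at r = 0.3, 0.5 and 0.7. With r = 0 it was unchanged (0.245 vs 0.246).

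**Chance imbalance.** One SE of baseline difference is √(1/50 + 1/50) = 0.20 SD or √(1/50 + 1/25) = 0.24 SD. With equal SDs, the part carried into the unadjusted result is r × 2 × that value:

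- 50 vs 50: 0.12-0.28 log2, a factor of 1.09-1.21 on the GMT ratio.
- 50 vs 25: 0.15-0.34 log2, a factor of 1.11-1.27.

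**Site.** This was simulated with four near-equal sites (52/52/26 subjects) and an assumed between-site SD of 0.3 of the within-site SD. Adding site moved the Group 1 vs 2 SE from 0.404 to 0.391 without baseline. With baseline at r = 0.3, 0.5 and 0.7 it moved from 0.389 to 0.374, 0.356 to 0.341 and 0.299 to 0.280. The cut is 3-6%. With no site differences the SE did not change.

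**The case against.** The strongest reply is that these are exploratory, PP-only models, conditional on normality, in a study that tests no formal hypothesis, and that the primary analysis is descriptive in mITT. Model 2A is unbiased under randomisation and its confidence interval already allows for chance baseline variation. Seroconversion, which is also modelled by schedule, already uses the pre-vaccination titer. All of this is correct. It limits the weight of the point but does not remove it, since SAP 8.1 brings the models into the primary section and no other planned titer comparison uses baseline.

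The relevant comparison is also with Model 2B, the model to be changed, where the gain could be near zero if r is 0.3. That stands. The larger figures above apply to Model 2A.

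The 15% loss applies to post-dose-3 assessments, so 50/50/25 is conservative for Day 22. Using the enrolled 60/60/30 as an upper bound, unadjusted power would be 78% and 60% rather than 70% and 53%. The relative SE gains do not change.

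Adding baseline to Model 2B would shrink the coefficients for prior vaccination and the other covariates where they act through baseline. This is a real cost, but a small one. IIV4 responses by these factors are reported in the stratified IIV4 summaries among Tables 40-67, and the covariate-effect objective in SAP 3.1.3 concerns H7N9, which would get no baseline term.

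The titles of Tables 96-99 are not wrong, because age, sex, BMI and vaccination history are baseline covariates. A reader could still assume that baseline titer is among them.

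On site, SAP 6.7 makes a deliberate choice, and the effect is small (0-6%). It remains secondary.

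**Conclusion.** The concern holds. The IIV4 linear models omit the Day 1 titer although the data exist and are a condition of the analysis populations. The consequence is lost efficiency and uncorrected chance imbalance, not systematic bias.

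The omission is certain from the text, but its size is not. At r near 0 there is no gain. Over r = 0.3-0.7 the gain runs from modest to substantial, and r may differ between 21 and 180 days. No precision gain is claimed for the logistic seroconversion models, and the baseline-titer point does not apply to H7N9. This should be corrected before the data are analysed, because adding baseline after an imbalance has been seen would be a post hoc choice. It does not threaten the validity of the trial.

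**What to change.** - Add the log Day 1 titer, specific to strain and assay, to Model 2B for the IIV4 strains. Handle values below 10 by the existing rule in SAP 4.5.2 ("for analysis are imputed as one-half the limit of detection", that is 5).
- Add site as a fixed effect to Model 2B for all strains, and amend SAP 6.7 to exempt these models from pooling. Descriptive and safety tables can stay pooled.
- Leave the H7N9 models without a baseline titer.
- Keep Model 2A unadjusted as the sensitivity analysis.
- Treat adjustment of the logistic models as optional. It makes the odds ratio conditional, and with four sites Group 3 has only about 25/4 ≈ 6 evaluable subjects per site.

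The cost is SAP wording, a baseline row in the Table 96-99 shells, site rows in Tables 92-99, and up to four degrees of freedom (one for baseline, up to three for site). No new data are needed. Two side effects should be stated in the SAP. Covariate coefficients in Tables 96-99 become conditional on baseline titer. And because SAP 6.3.2 asks for HAI or Neut results, a subject with a baseline for one assay only would drop out of Model 2B for the other.

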8.3.3. NA Serum Antibody Responses

Descriptions of the NA assays and planned analyses will be described in an addendum to this SAP.

9. SAFETY EVALUATION

All summaries and analysis of safety data will be presented for the Safety Analysis Population. Safety summaries will be presented overall and grouped by treatment group.

Continuous variables will be summarized using the following descriptive statistics: n (non-missing sample size), mean, standard deviation, median, maximum and minimum. All categorical measures will be summarized by the frequency and percentages of observed levels will be reported for all categorical measures. The denominator for the percentages may be based on the number of non-missing observations for an assessment or based on the number of subjects in a population. This will be described for each table.

9.1. Demographic and Other Baseline Characteristics

Summaries of age, sex, ethnicity, race, BMI, and prior receipt of seasonal influenza vaccine will be presented by site ([Table 23](#), [Table 24](#)) and by treatment group ([Table 25](#), [Table 26](#)). Age will be summarized as a continuous variable. Ethnicity is categorized as Hispanic or Latino, or not Hispanic and not Latino. In accordance with NIH reporting policy, subjects may self-designate as belonging to more than one race or may refuse to identify a race, the latter reflected in the electronic case report form (eCRF) as “No” to each racial option. BMI will be summarized as a continuous as well as categorical variable, categorized as (<30, ≥30). Self-reported history of prior receipt of seasonal influenza vaccine will be categorized as follows: received 2016-2017 seasonal vaccine, did not receive 2016-2017 seasonal vaccine, or unknown. Demographic information for individual subjects will be provided in [Listing 6](#). Subjects’ prior influenza vaccination history (seasonal and non-seasonal) will be provided in [Listing 8](#).

